#### PK assessment following 3-month daily prophylaxis in Cohort 1 and 2 patients

Patients completing the 3-month daily prophylactic part will attend the study site. The following assessments will be performed:

• After a wash-out of at least 72 hours after the last OCTA101 injection, or any other FVIII injection, a dose of 50 IU/kg OCTA101 sc will be administered

• Blood sample for FVIII inhibitor measurement (modified Nijmegen Bethesda assay), (before and at 21 days after the injection)

• Blood sample for anti-OCTA12 measurement, (before and at 21 days after the injection)

Octapharma AG	
Name of Investigational Product: OCTA101 (Human-cl rhFVIII and recombinant human von Willebrand Factor fragment dimer)	Protocol Identification Code: SubQ8-01
Name of Active Ingredient: Coagulation factor VIII	Date of Final Protocol: 30-Jul-2021

 
2°h, 4 h, 8 h, 12 h, 24 h, 48 h, 72 h, 96 h, and 120
 
Blood sample for OCTA12 measurement, (befo 96 h, 120 h, 7 days, 14 days, and 21 days after the Physical examination (at End of Study)
 
Assessment of local injection site reactions (direinjection)
 
Adverse event monitoring throughout the study
 
Documentation of concomitant medication throughout the study
 
	) h after the injection) re and, 2 h, 4 h, 8 h, 12 h, 24 h, 48 h, 72 h, e injection) ectly after injection and $15 \pm 5$ min post- period ughout the study period with Nuwia iv prophylaxis, patients are

Patients in Cohort 6 will have their first Nuwiq administered at the study site. After the runin period, patients will be trained in sc OCTA101 self-administration for subsequent home administration.

The following assessments will be performed:

Start of 4 to 6 week Nuwiq run-in:

- Documentation of bleeding episodes and their treatment throughout the run-in period
- Adverse event monitoring throughout the run-in period
- Documentation of concomitant medication throughout the run-in period

Daily OCTA101 treatment periods:

• Vital signs (before and 8 h after the injection OCTA101 at the beginning of each dosing period and 0.5, 1, 2, 3, 4, 5 and 6 months thereafter)

• Routine safety lab (before and 8 h after the OCTA101 injection at the beginning of each dosing period and 0.5, 1, 2, 3, 4, 5 and 6 months thereafter)

• Blood sample for FVIII inhibitor measurement (modified Nijmegen Bethesda assay), (before the first injection of OCTA101 and 0.5, 1, 2, 3, 4, 5 and 6 months thereafter for each of the 6-7 month OCTA101 daily prophylaxis treatment periods)

• Blood sample for anti-OCTA12 measurement, (before the first injection of OCTA101 and 0.5, 1, 2, 3, 4, 5 and 6 months thereafter for each of the 6-7 month OCTA101 daily prophylaxis treatment periods)

Name of Sponsor/Company: Octapharma AG		
Name of Investigational Product: OCTA101 (Human-cl rhFVIII and recombinant human von Willebrand Factor fragment dimer)	Protocol Identification Code: SubQ8-01	sion
Name of Active Ingredient: Coagulation factor VIII	Date of Final Protocol: 30-Jul-2021	

• Blood sample for FVIII:C measurement (one-stage and chromogenic assay), (before and 8°h after the OCTA101 injection at the beginning of the 6-7 month dosing periods and 0.5, 1, 2, 3, 4, 5 and 6 months thereafter)

- Blood sample for OCTA12 measurement, (before the first injection of OCTA101 and 0.5,
- 1, 2, 3, 4, 5 and 6 months thereafter for each dosing period)
- Physical examination (at End of Study)
- LumiTope assay (before the first injection of OCTA101 and 0.5, 1, 2, 3, 4, 5 and 6 months thereafter for each dosing period)
- Assessment of local injection site reactions (directly after injection and  $15 \pm 5$  min postinjection, for each injection)
- Documentation of bleeding episodes and their treatment throughout the study period
- Adverse event monitoring throughout the study period
- Documentation of concomitant medication throughout the study period

#### Unscheduled Visits

In case of positive inhibitor results, inhibitor retesting using a second, separately drawn sample should be performed, preferably within 15 days of becoming aware of the positive result. Other reasons for unscheduled visits may be the occurrence of serious AEs or hospitalizations due to severe bleeding episodes.

#### Stopping rules

A single death event (with the exception of death from underlying disease or any other death clearly unrelated to OCTA101) that occurs within 30 days of administration of study drug.

According to the revised stopping rules implemented by Amendment 2, the study was to be put on hold until a further DMC recommendation for further conduct of the study was made, if more than one patient met the following criteria:

• Exhibits a consistently high titer FVIII inhibitor ( $\geq$ 5 BU), as determined by central laboratory tests including a retest as detailed in Section 6.1.9.

or

• Exhibits a low titer FVIII inhibitor ( $\geq 0.6$  BU and < 5 BU), as determined by central laboratory test, including a retest as detailed in Section 6.1.9, and a standard recovery test using intravenous factor VIII shows a recovery below 66%. A formal half-life study with determination of the terminal half-life ( $t_{1/2}$ ) associated with the recovery study is encouraged with the patient in a non-bleeding state and free of any intercurrent illness.

As a further patient with FVIII inhibitors in Cohort 2 subsequently met these criteria, the study was put on hold and patients stopped OCTA101 treatment. The ongoing patients in

Name of Sponsor/Company: Octapharma AG		
Name of Investigational Product: OCTA101 (Human-cl rhFVIII and recombinant human von Willebrand Factor fragment dimer)	Protocol Identification Code: SubQ8-01	sion
Name of Active Ingredient: Coagulation factor VIII	Date of Final Protocol: 30-Jul-2021	

Cohort 3 were switched to Nuwiq prophylaxis for the remainder of the planned 3-month prophylaxis period.

Once Cohort 6 has been initiated, all patients will immediately stop treatment with OCTA101, if another patient develops a confirmed FVIII inhibitor ( $\geq 0.6$  BU).

In this case, all FVIII inhibitor negative patients will switch to prophylactic treatment with Nuwiq comparable to the run-in phase, and will come for a final follow-up visit after treatment change. During the final follow-up visit the following should be done:

- Routine safety lab
- Blood sample for FVIII inhibitor measurement (modified Nijmegen Bethesda assay)
- Blood sample for anti-OCTA12 measurement
- Blood sample for OCTA12 measurement
- Physical examination
- LumiTope assay
- Documentation of bleeding episodes and their treatment
- Adverse event monitoring
- Documentation of concomitant medication

#### Statistical Analysis Plan:

Safety and tolerability data will first be analyzed for each cohort after the first dose(s) and evaluated by an external DMC. Two separate analyses will be performed: the first one will include all available data of enrolled patients in Cohorts 1, 2, 3, and 5 and the second one will include all data of the newly defined Cohort 6. Analyses based on data from repeat dosing

Protocol Identification Code: SubQ8-01	ission
Date of Final Protocol: 30-Jul-2021	
	Protocol Identification Code: SubQ8-01 Date of Final Protocol: 30-Jul-2021

from Cohort 1, 2, and 3 with OCTA101 for 3 months will be analyzed separately from data related to the first doses. In these analyses, data will be presented by cohort and overall. Analysis based on Cohort 6 data will be presented by period (run-in period with Nuwiq and OCTA101 treatment period) and by planned OCTA101 daily dose.

For each cohort

- Descriptive analysis of demographic and baseline variables.
- Safety analyses

The number and percentage of patients with AEs and the number of AEs will be summarized by primary MedDRA System Organ Class (SOC) and Preferred Term (PT). Separate tables showing all AEs, all serious AEs and all AEs at least possibly related to IMP will be generated. Further a summary of AEs by severity, presenting the most severe event per patient overall and within each SOC and PT will be generated.

For thromboembolic events and local injection site reactions, appropriate clusters of MedDRA terms will be defined and such events will be presented within these clusters, using the summaries detailed above.

The frequencies of local injection reactivity ratings by the investigator and the patient will be summarized over time periods. The frequencies (including percentages) of any inhibitor formation to FVIII and antibody formation to OCTA12 will be presented. Vital sign and safety laboratory parameters will be analyzed using descriptive statistics for measured values and for changes from pre-dose values to each single injection.

- Individual non-compartmental individual PK analyses (NCA) of the time courses of FVIII:C (after administration of OCTA101 and Nuwiq) and OCTA12 (administration of OCTA101) including terminal half-life ( $t_{1/2}$ ), incremental in-vivo recovery (IVR), maximum plasma concentration ( $C_{max}$ ), time for reaching maximum plasma concentration ( $t_{max}$ ), mean residence time (MRT), quantifiable and total area under the concentration time curve (AUC), apparent clearance (CL), apparent distribution volume (Vd). In addition, for descriptive purposes, the time courses of FVIII:C and OCTA12 may be analyzed compartmentally assuming a linear, open, one- or two-compartment model. Exposure levels will be reported untransformed and standardised for dose and body weight.
- In addition, for patients from Cohorts 1 to 3 and Cohort 6: FVIII:C trough and peak levels during, and after for Cohorts 1 and 2, the 3-month daily dosing will be graphically displayed and listed by patient.

Name of Investigational Product: OCTA101 (Human-cl rhFVIII and recombinant human yon Willabrand Easter fragment dimer)Protocol Identification Code: SubQ8-01	Name of Sponsor/Company: Octapharma AG		
	Name of Investigational Product: OCTA101 (Human-cl rhFVIII and recombinant human von Willebrand Factor fragment dimer)	Protocol Identification Code: SubQ8-01	ission
Name of Active Ingredient: Coagulation factor VIIIDate of Final Protocol: 30-Jul-2021	Name of Active Ingredient: Coagulation factor VIII	Date of Final Protocol: 30-Jul-2021	

- In addition, for patients from Cohort 3: Estimation of relative bioavailability of FVIII:C by the ratios of AUC after sc administration over AUC after iv administration.
- Data from Cohort 5 covering the pharmacokinetics after single sc doses of 20, 40 and 60 IU/kg OCTA101 will be used to derive estimates of the dose-proportionality of the pharmacokinetics of FVIII:C and OCTA12.
- Quantifiable and  $\lambda_z$ -extrapolated time courses of the concentrations after single doses (all cohorts) will be used to simulate the time courses when defined doses would be administered repeatedly at specified interval.

The total annualized bleeding rate, the spontaneous annualized bleeding rate, the traumatic annualized bleeding rate, the total annualized treated bleeding rate, the spontaneous annualized treated bleeding rate, and the annualized joint bleeding rate during the daily sc treatment with OCTA101 will be presented for patients in the FAS and PP set in Cohort 6, grouped by dose level of daily OCTA101 dosing. These bleeding rates will be compared descriptively to those derived from the bleeding frequencies in the previous 6 months prior to the study. For the daily dosing period of Cohorts 1 to 3, no bleeding rates were calculated, because none occurred during daily prophylaxis with OCTA101. The observation period was considerably shorter than planned due to the study stop.

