- After 3 months of treatment with OCTA101, the patients had their 3-month follow-up visit. During the 2 to 3 weeks waiting for all relevant results, especially FVIII inhibitor testing results, these patients continued on daily dosing with 12.5 IU/kg OCTA101 sc.
- DMC agreed that further patients can start their daily prophylaxis with OCTA101, up to 16 patients proceeded with 12.5 IU/kg OCTA101. After further 3 months, following DMC data review, the first 3 patients of this cohort were planned to start on daily dosing with 25 IU/kg OCTA101 sc for 6-7 months. The remaining patients were planned to follow after a further 3 months, after DMC data review.
- Patients reporting two spontaneous bleeding episodes will be switched to the next higher dose level after having completed at least 3 months with 12.5 IU/kg OCTA101 daily treatment: they will start daily dosing with 25 IU/kg OCTA101 sc.

Name of Sponsor/Company: Octapharma AG		
Name of Investigational Product: OCTA101 (Human-cl rhFVIII and recombinant human von Willebrand Factor fragment dimer)	Protocol Identification Code: SubQ8-01	silor
Name of Active Ingredient: Coagulation factor VIII	Date of Final Protocol: 30-Jul-2021	

- Depending on the results of the 12.5 IU/kg and 25 IU/kg OCTA101 treatment phases, the initiation of a 40 IU/kg OCTA101 phase will be considered together with the DMC.
- Bleeding episodes will be controlled with the use of Nuwiq during the entire duration of treatment in Cohort 6.

The cohorts are summarized as follows:

• Cohort 1: 50 IU/kg OCTA101 (n=4): Single-period investigation with a single sc dose of 50 IU/kg OCTA101 profiled up to 72 hours after dosing.

DMC assessment after last patient of Cohort 1. If ok, proceed with Cohort 2, and also with daily prophylactic dosing (approximately 40-60 IU/kg) for 3 months (initially with Nuwiq but then with OCTA101 if advised by the DMC). Patients from Cohort 2 and 3 may also start their daily prophylactic dosing for 3 months immediately after collection of the last PK sample.

- Cohort 2: 100 IU/kg OCTA101 (n=4): Single-period investigation with a single sc dose of 100 IU/kg OCTA101 profiled up to 96 hours after dosing. DMC assessment after last patient of Cohort 2. If ok, proceed with Cohort 3.
- Cohort 1 and 2: PK assessment after 3-month daily dosing (n=8): single-period investigation with a single sc dose of 50 IU/kg OCTA101 profiled up to 120 hours after dosing for FVIII and up to 21 days for OCTA12.

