- Cohort 3: 50 IU/kg OCTA101 (n=8): Two-period investigation of a single iv dose of 50 IU/kg Nuwiq profiled for up to 72 hours after dosing followed by sc dose of 50 IU/kg OCTA101 administered into the abdomen profiled up to 72 hours. Treatments were to be administered in fixed sequence, with Nuwiq first.

DMC assessment after last patient of Cohort 3. If ok, proceed with Cohort 4 and 5.

- **Cohort 4:** 50 IU/kg OCTA101 (n=4): Cancelled.
- **Cohort 5:** (n=4) [8 had been planned]: Three-period investigation of single sc doses of 20, 40, and 60 IU/kg OCTA101 profiled up to 72 hours after dosing. Treatments were to be administered in fixed dose-ascending sequence.
- Cohort 6 (n≥16): Following an initial 4 to 6-week run-in period with Nuwiq iv prophylaxis, >3-6 months daily prophylactic treatment with 12.5 IU/kg OCTA101 sc, then 25 IU/kg OCTA101 sc for a further 6-7 months (exact dosing depends on available vial sizes). In case of two spontaneous bleeding episodes, after having completed at least 3 months with 12.5 IU/kg OCTA101 daily treatment the individual treatment dose will be increased from 12.5 to 25 IU/kg. Site of administration

Name of Sponsor/Company: Octapharma AG		
Name of Investigational Product: OCTA101 (Human-cl rhFVIII and recombinant human von Willebrand Factor fragment dimer)	Protocol Identification Code: SubQ8-01	ssio
Name of Active Ingredient: Coagulation factor VIII	Date of Final Protocol: 30-Jul-2021	

(abdomen or thigh) to be chosen by the patient. A further treatment phase with 40 IU/kg OCTA101 will be discussed with the DMC, once results of earlier dosing phases are available.

The DMC will review and assess the available results approximately every 3 months.

By DMC-recommendation, patients enrolled in Cohorts 1, 2, and 3 proceeded to 3-month prophylactic treatment part of the study and received daily dosing using one injection (approximately 40-60 IU/kg; dose chosen to allow administration by single injection; it was permitted to daily alternate the vial size, e.g. 3000 IU on one day 1, 5000 IU on day 2, 3000 IU on day 3, 5000 IU on day 4 etc.) of OCTA101 for 3 months (home treatment). Patients from Cohort 1 received prophylactic Nuwiq (home treatment) until the DMC had confirmed that OCTA101 can be used as daily prophylaxis. Bleeding events during the study were treated with Nuwiq. Throughout this part of the study, FVIII inhibitors, plasma concentrations of FVIII:C, and OCTA12 were measured repeatedly.

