## 9.2.2 Efficacy Analysis Plan

Property

Pharmacokinetic data will be analysed separately for each dose cohort.

Blood for the determination of the concentrations of FVIII:C (one-stage and chromo-genic assays) and OCTA12 in plasma will be sampled at scheduled times. The time courses of the plasma concentrations will be analysed non-compartmentally using the following conventions:

• The courses of the concentrations are analysed individually relative to the actual time of sampling (relative to the time of first injection).

- For the analysis, non-quantifiable pre-dose levels will be set equal to zero. In the event of quantifiable levels prior to first dosing, the baseline level will be subtracted from the post-dosing values and the further analysis is focused on the post-dosing changes from baseline.
- Post-dosing values that are either missing or not quantifiable will not be included in the analysis.

- Extrapolations beyond the last quantifiable plasma concentration will only be re-ported if the apparent terminal log-linearity used to this purpose is sufficiently well expressed for at least 3 data points.
- The duration of profiling is adjusted by dose; based on the available experience with rFVIII it may be expected that the quantifiable area under the time course of the concentrations (AUC) is at least 80% of the total i.e. extrapolated AUC.
- The time courses of the plasma concentrations will be summarised descriptively by means of the following non-compartmental metrics:
  - Cmax: maximum observed concentration
  - $T_{max}$ : time of occurrence of  $C_{max}$  after dosing
  - AUC(0-tz): quantifiable area under the time course of the concentrations de-rived by means of the combined linear/log-linear trapezoidal rule
  - $-\lambda_z$ : apparent terminal log-linear rate constant
  - $t_{\frac{1}{2}}$ : apparent terminal log-linear half-life
  - AUC( $t_z$ - $\infty$ ): AUC extrapolated beyond the last time point with quantifiable concentrations calculated as C\*( $t_z$ )/ $\lambda_z$  in which C\*( $t_z$ ) is the concentration at time  $t_z$  fitted according to  $\lambda_z$
  - AUC( $(0-\infty)$ ): total AUC = AUC( $(0-t_z)$ + AUC( $(t_z-\infty)$ )
  - AUCextrapolated: extent of AUC extrapolation = AUC( $t_z$ - $\infty$ )/AUC(0- $\infty$ )
  - AUMC(0-tz) and AUMC(0-∞): quantifiable and total area under the statistical first moment curve
  - MRT: mean residence time =  $AUMC(0-\infty)/AUC(0-\infty)$

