- Cohort 1 and 2 PK assessment after 3-month daily dosing (n=8): single-period investigation with a single sc dose of 50 IU/kg OCTA101 profiled up to 120 hours after dosing for FVIII and up to 21 days for OCTA12.
- Cohort 6 (n=16): following an initial 4 to 6-week run-in period with Human-cl rhFVIII iv prophylaxis, 3-month daily prophylactic treatment with 12.5 IU/kg OCTA101 sc, then 25

CONFIDENTIAL

04-Mar-2021

IU/kg OCTA101 sc, and then 40 IU/kg OCTA101 sc (exact dosing depends on vial strength). The analysis of this data is not in the scope of this SAP.

By DMC-recommendation, patients enrolled in Cohorts 1, 2, and 3 proceeded to 3-month prophylactic treatment part of the study and received daily dosing using one injection (approximately 40-60 IU/kg; dose chosen to allow administration by single injection; it was permitted to daily alternate the vial size, e.g. 3000 IU on one day 1, 5000 IU on day 2, 3000 IU on day 3, 5000 IU on day 4 etc.) of OCTA101 for 3 months (home treatment). Patients from Cohort 1 received prophylactic Human-cl rhFVIII after the initial PK assessment (home treatment) until the DMC had confirmed that OCTA101 can be used as daily prophylaxis. Bleeding events during the study were to be treated with Human-cl rhFVIII. Throughout this part of the study, FVIII inhibitors, plasma concentrations of FVIII:C, and OCTA12 were measured repeatedly.

A PK assessment was performed in all patients from Cohorts 1 and one patient from Cohort 2 who completed their 3-month daily injection period for further characterizing the PK of FVIII:C and OCTA12. Blood samples were collected up to 21 days in order to see a decline in OCTA12 plasma concentrations (and allow determination of half-life) as the initial PK period was not long enough to see a decline of OCTA12. Concomitant measurement of FVIII:C up to 120 h will allow evaluation of any interaction between OCTA12 plasma concentration and FVIII:C.

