8.1 Specifications related to whole analysis

8.1.1 Tables

If not explained differently below, summary tables will be stratified by cohort and by product/dose if applicable.

Summary tables for single dose cohorts will be presented showing the result of each cohort in the same summary table.

Summary tables related to data collected during the 3-month daily dosing period will be based on the overall FAS and will not be stratified by the previous cohort.

For continuous data, the basic statistics sample size, (number of missing values), mean, and standard deviation; minimum, first quartile, median, third quartile and maximum will be shown. Categorical data will be displayed in frequency tables showing sample size and absolute and relative frequency. The time course of continuous data will be presented using the basic statistics for each visit and the differences from baseline to last value and relative differences from baseline to last value.

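### First-dose OCTA12 AUC(0-tz) is cut off at 96 h in Cohort 2 and at 72 h in the other cohorts, so a dose-normalised comparison across cohorts carries a window effect of about 25-78%

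*Protocol*

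**What the plan says.** **Windows.** The Study Outline describes Cohort 1 as "Single-period investigation with a single sc dose of 50 IU/kg OCTA101 profiled up to 72 hours after dosing", Cohort 2 as "Single-period investigation with a single sc dose of 100 IU/kg OCTA101 profiled up to 96 hours after dosing", and the sc dose of Cohort 3 as "administered into the abdomen profiled up to 72 hours". All three Cohort 5 periods also end at 72 h.

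**Parameters.** The analysis outline in the protocol's Study Outline lists "quantifiable and total area under the concentration time curve (AUC") among the individual non-compartmental parameters for FVIII:C and OCTA12. Protocol 9.2.2 and SAP 5.4.2 define AUC(0-tz) up to the last quantifiable concentration. No partial AUC with a fixed end point appears in either document. Protocol 9.2.2 reports exposure both untransformed and standardised for dose and body weight, and SAP 8.9.1 explains how the dose adjustment is made.

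**Reason for unequal windows.** Protocol 9.2.2 says "The duration of profiling is adjusted by dose" and expects the quantifiable AUC to be at least 80% of the total. It bases that on experience with rFVIII. No such case is made for OCTA12. SAP 5.2 explains the later 21-day sampling of OCTA12 by saying that it was needed "as the initial PK period was not long enough to see a decline of OCTA12".

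**Presentation.** SAP 8.1.1 states: "Summary tables for single dose cohorts will be presented showing the result of each cohort in the same summary table". SAP 8.9.1 adds non-compartmental parameter tables for Cohorts 1, 2 and 3 and for each Cohort 5 period.

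**The concern.** Where most of a curve lies inside the sampling window, AUC(0-tz) depends little on when sampling stops. Where the analyte has not started to fall, AUC(0-tz) mainly measures how long it was sampled. By the SAP's own account, OCTA12 after a first dose is in the second situation.

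The total AUC may not rescue the comparison. Protocol 9.2.2 allows extrapolation only when a log-linear terminal phase is well expressed on at least three points, and a profile without decline does not supply one. SAP 8.9.3 seems to anticipate this, because it models AUC(0-tz) for OCTA12 but not for FVIII:C.

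Dividing by dose invites the reader to compare 100 IU/kg with the lower doses. The extra 24 h in Cohort 2 would then look like a departure from proportionality. OCTA12 pharmacokinetics is a secondary objective, so at stake is the correct reading of a secondary summary. No formal test is affected.

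**Working it through.** **The plan's own figure.** The 80% expectation comes without a formula, so I checked it for consistency only. The model has one compartment with first-order absorption:

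AUC(0-T) = [ka/(ka-k)] x [(1-exp(-kT))/k - (1-exp(-ka T))/ka], with ka solved from tmax and covered share = k x AUC(0-T).

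Protocol 1.2 gives an sc FVIII:C half-life of 25.3 h in minipigs and a peak at about 6 h in both animal models. These give 85.3% covered at 72 h and 92.4% at 96 h. Coverage at 72 h stays above 80% up to a half-life of about 30 h. For FVIII:C the expectation is reasonable. The factor AUC(0-96)/AUC(0-72) is 1.08, or 1.01 with a 12 h half-life (Protocol 1.1 cites 12-14 h for VWF-bound FVIII).

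**OCTA12.** The documents give neither half-life nor tmax. I assumed half-lives of 3-14 days with tmax 24-96 h, and also profiles that do not decline. Write w = AUC(0-96)/AUC(0-72). With identical linear kinetics, the dose-normalised Cohort 2:Cohort 1 ratio should be 1.00, and AUC(0-tz) gives w instead. The untransformed ratio should be 2.00 (100/50), and AUC(0-tz) gives 2w.

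Worked case, half-life 3 days and tmax 24 h: k = ln2/72 = 0.00963 per h and ka = 0.1118 per h. The covered share is 45.3% at 72 h and 56.6% at 96 h, so w = 0.566/0.453 = 1.25.

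| Assumed OCTA12 profile | Covered at 72 h | w | 2w |
|---|---|---|---|
| Half-life 3 d, tmax 24 h | 45% | 1.25 | 2.50 |
| Half-life 3 d, tmax 96 h | 17% | 1.52 | 3.05 |
| Half-life 14 d, tmax 24 h | 13% | 1.33 | 2.65 |
| Half-life 14 d, tmax 96 h | 8% | 1.49 | 2.97 |
| Flat: 96/72 | n/a | 1.33 | 2.67 |
| Linear rise to plateau at 24 h: 84/60 | n/a | 1.40 | 2.80 |
| Linear rise to plateau at 72 h: 60/36 | n/a | 1.67 | 3.33 |
| Linear rise throughout: (96/72)^2 | n/a | 1.78 | 3.56 |

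The lowest value comes from a profile that falls by 21% between 72 h and 96 h. That fits poorly with the SAP's remark that no decline was seen, so 1.33 and above is closer to what the SAP describes.

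**How much is window and how much is dose.** The window's share of the untransformed log-ratio is ln(w)/ln(2w): 0.24 for w = 1.25 and 0.45 for w = 1.78. Dose accounts for the other 55-76%. After dose normalisation the whole excess is window.

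**Cmax.** If OCTA12 still rises linearly at 72 h, the maximum to 96 h is 96/72 = 1.33 times the maximum to 72 h. With tmax at or before 72 h there is no effect.

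**Sampling grid.** Cohorts 1 and 2 have a 0.5 h sample and none at 12 h. Cohort 3 sc and Cohort 5 have the reverse. With the linear/log-linear trapezoidal rule on those times, AUC(0-72 h) differs by about 1% or less.

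**First against repeat profile.** I simulated 90 equal daily doses, a 72 h wash-out (the protocol's minimum) and one further equal dose, with unchanged kinetics and the same assumed half-lives and tmax. The residual level before the last dose is about 3-23 times the single-dose Cmax. The repeat:first ratio of AUC(0-72 h) is then -0.1 to -1.3 with the baseline subtraction of Protocol 9.2.2 and SAP 8.9, and about 4 to 32 without it.

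**After the fix.** On a common 0-72 h window w = 1.00, so under linear kinetics the first-dose ratios return to 1.00 and 2.00.

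**The case against.** The strongest reply is that the plan rarely puts the unequal windows against each other, and much of this stands.

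- Protocol 9.2.2 analyses PK separately by cohort. SAP 8.1.1 is a default that yields to more specific text, and SAP 8.9.1 asks for parameter tables by cohort and period. But separate calculation does not prevent a side-by-side reading of dose-adjusted values.
- A reader might infer that OCTA12 differences between cohorts are largely sampling time. The documents do not support that for untransformed values: only Cohort 2 (n=4) has a different first-dose window, and dose explains most of the difference.
- A reader might infer that the dose-proportionality result is compromised. It is not: SAP 8.9.3 uses Cohort 5 alone, with one 72 h schedule. The Cohort 3 bioavailability comparison also uses 72 h for both routes.
- A reader might infer that the 21-day repeat profile will produce false accumulation against the first profile. No such AUC comparison is specified, and the repeat PK is treated as its own analysis. Carry-over and baseline subtraction would make the comparison uninterpretable whichever window is used.
- A reader might infer harm to Phase 3 dosing. Protocol 3.3.1 ties that to FVIII:C trough levels, where the window effect is small.
- SAP 8.9.1 tabulates concentrations by time point, so shared times can be compared directly. That helps a careful reader but does not correct the summary parameter.

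**Conclusion.** The point holds in a limited form. First-dose OCTA12 AUC(0-tz) is a truncated area, and Cohort 2 was sampled 24 h longer than Cohorts 1, 3 and 5. Under identical linear kinetics its dose-normalised value in Cohort 2 would exceed theirs by about 25-52% in the one-compartment range, 33% if flat, and up to 78% if rising linearly. These figures rest on assumed OCTA12 profiles, although any profile that does not decline gives at least 33%. The window effect for FVIII:C (about 1-8%) and the grid effect on AUC (about 1%) are minor and would not justify a change alone. This is a cheap improvement to a descriptive secondary summary.

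**What to change.** In SAP 5.4.2 and 8.9.1 and in Protocol 9.2.2:

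1. Add OCTA12 AUC(0-72 h) and Cmax within 0-72 h for every first-dose sc profile, optionally for FVIII:C as well, using all samples up to 72 h. Interpolate AUC to nominal 72 h, because Protocol 6.1.12 allows 3 h either way and the analysis uses actual times. State the rule for a final sample taken before 72 h.
2. Use these parameters for any side-by-side or dose-normalised reading across cohorts.
3. Keep AUC(0-tz), and show its tz wherever it is reported.
4. State that neither AUC(0-72 h) nor AUC(0-tz) will be used to compare first with repeat OCTA12 profiles, because of carry-over and baseline subtraction.

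The cost is one or two derived parameters from samples already taken, plus a few lines of text. The new parameters ignore Cohort 2 data after 72 h, which stay in the existing ones. If the tables have already been produced, the addition can be labelled post hoc.
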